12.3 Budget

| Item | Unit(s) required | Unit Price(KSh) | Amount (KSh) |
|---|------------------|-----------------|----------------|
| Ethics and Scientific Review | | | |
| Ethical clearance fee (AMREF) | - | - | 5,000 |
| Research approval by NACOSTI | - | - | 2,000 |
| Sub-total | - | - | 7,000 |
| Protocol costs | | | |
| ISO 26642 standard | 1 | 9,000 | 9,000 |
| Sub-total | - | - | 9,000 |
| Training Costs | | | |
| Training of 2 enumerators (2 days) | 2 | 2,200 | 4,400 |
| Meeting with phlebotomy team | 2 | 6,300 | 12,600 |
| Transport | 6 | 600 | 3,600 |
| Sub-total | - | - | 20,600 |
| Data collection costs | | | |
| Phlebotomy (4 days & 2 phlebotomists) | 8 | 7,640 | 61,120 |
| Team leader (4 days) | 2 | 7,640 | 15,280 |
| PhD student (4 days) | 4 | 7,640 | 30,560 |
| Enumerators (4 days) | 8 | 2,540 | 20,320 |
| Driver (4 days) | 4 | 5,135 | 20,540 |
| Fuel | | 20,000 | 20,000 |
| Participant lunch (3 days) | 30 | 500 | 15,000 |
| Community mobiliser (4 days) | 4 | 2,240 | 8,960 |
| Stationery (paper for VAS scores) | 1 | 500 | 500 |
| 2 dozen pens | 2 | 300 | 600 |
| Water (crates) | 4 | 800 | 3,200 |
| Airtime (4 study days) | 4 | 500 | 2,000 |
| Subtotal | | | 198,080 |
| Equipment and Consumables Costs | | | |
| Blood pressure measurement | | | |
| OMRON blood pressure monitor (digital, M2) | 1 | 8,500 | 8,500 |
| Subtotal | | | 8,500 |
| Collection, handling, storage and transfer of blood samples | | | |
| Butterfly needles (preferably size 21G;22G;23G) | 80 | 1500/100pc pkt | 1,500 |
| Flexible IV tube | 80 | 200 | 16,000 |
| Vacutainer tubes | 2 | 1,200/100pcs | 2,400 |
| Vacutainer holder | 10 | 250 | 2,500 |
| Alcohol swabs | 80 | 180/100 pieces | 180 |
| Disposable rubber gloves | 1 | 250/100 pieces | 250 |

| | | | |
|--|----|---------------|---------------|
| Bio-hazard box | 2 | 50/pc | 100 |
| Biological waste disposal bag (20l) | 3 | 15 | 45 |
| Hand sanitizer | 1 | 500 | 500 |
| Cryogenic vials (freezable) | 2 | 1,200/100pcs | 2,400 |
| Disposable pipettes or pipettes with changeable apex | 2 | 4,500 | 9,000 |
| Blue tips | 1 | 1,200/1000pcs | 1,200 |
| Centrifuge, 12 tubes with timer | 1 | 20,000 | 20,000 |
| Permanent marker pens | 4 | 250 | 1,000 |
| Cool boxes (Thermos, 28lit) | 2 | 3,000 | 6,000 |
| Ice packs | 10 | 400/pc | 4,000 |
| Liquid nitrogen | 50 | 480/kg | 24,000 |
| Subtotal | | | 91,075 |

Anthropometric and body composition measurements

| | | | |
|--|----|-----------|----------------|
| Tefal Weight scale | 4 | 4,000/pc | 16,000 |
| Seca portable/wall mounted stadiometer with movable head piece, or measuring rod | 4 | 7,000/pc | 28,000 |
| Waist circumference tape | 10 | 1000/pc | 10,000 |
| Bodystat 500 | 1 | 80,000/32 | 80,000 |
| Subtotal | | | 134,000 |

Laboratory Blood Specimen Analysis Costs

| | | | |
|---|-----|-------|------------------|
| Blood glucose (30 fasting, 180 random) | 210 | 649 | 136,290 |
| Plasma insulin (fasting) | 30 | 3,849 | 115,470 |
| Plasma insulin (non-fasting) | 180 | 4,149 | 746,820 |
| C-peptide (fasting/non-fasting) | 20 | 2,949 | 58,980 |
| HbA1C | 20 | 2,949 | 58,980 |
| Lipid profile (Cholestrol, HDL,LDL,Trig+Ratio calculations) | 20 | 2,949 | 58,980 |
| Subtotal | | | 1,175,520 |
| TOTAL | | | 1,643,775 |
| Miscellaneous (flat rate) | | | 10,000 |
| GRAND TOTAL | | | 1,653,775 |

Funding: VLIR-UoS

Appendix 2: Questionnaire for glyceimic and insulinemimic response study.

Study N^o:

Participant code #:

Date:

Answer the following questions. Please tick [✓] one

1. Do you have a history of eating disorders and/or irregular eating habits? Yes []
No []
2. Do you currently use tobacco or alcohol? Yes [] No []
3. Are you on your menstrual period or having adverse premenstrual symptoms? Yes []
No []
4. Are you currently consuming any supplements? Yes []
No []
(What, when, dose, manufacturer/brand)
5. Are you currently on any medication? Yes []
No []
(What, when, dose, manufacturer/brand)

Participant information, anthropometry and body composition

| | | | | |
|----------------------|-------------------|-------------------------|-------------|------------|
| Gender (tick one) | DOB (DD/MM/YY) | Blood pressure | Waist circ. | Hip circ. |
| M[] F[] | ___/___/___ | _____ mmHg | _____ cm | _____ cm |
| Weight | Height | BMI | Impedance | Resistance |
| _____ kg | _____ cm | _____ kg/m ² | | |

24 hour dietary recall

1. Is this a typical day? Please tick [✓] one. Yes [] No []
If not, give an example of a typical day after yesterday's record if you wish.

E.g.

| Time | Quantity eaten | Details of food and drink |
|---------------|-----------------------|--|
| 7:15am | 1 cup | Tea |
| | | Milk |
| | 1½ teaspoons | White sugar |
| | ½ glass | Water |
| 10am | 1 mug | Wheat porridge |
| | 2 | Medium sized yellow sweet potatoes (boiled) |

| | | |
|--|--|--|
| | | |
| | | |
| | | |
| | | |

Blood draw

Time of catheter introduction: _____

Time of first blood draw: _____

Start of test food consumption: _____

Completion of test food consumption:

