7. STUDY DESIGN AND SAMPLING STRATEGY

7.1 Glyceimic index (GI) and glyceimic response study

The GI evaluates the blood-raising ability of equi-carbohydrate portions of different single foods or mixed meals. To assess the GI of the common bean product *in vivo*, 10 healthy volunteers will be recruited. The selection of the number of participants, and the inclusion and exclusion criteria is based on the ISO_26642_2010 standard [53].

The 10 healthy volunteers will be recruited from Jomo Kenyatta University of Agriculture and Technology (JKUAT) and handled at the JKUAT University Hospital.

Inclusion criteria:

- Male or female 18-69 years
- No known food allergies or intolerances
- No prescription medication² (excluding oral contraceptives) known to affect glucose intolerance (e.g. steroids, protease inhibitors, antipsychotics e.t.c.)

Exclusion criteria

- Known history of diabetes mellitus or use of anti-hyperglycaemic medication or insulin
- Alcohol or tobacco use in the evening preceding the test
- Vigorous exercise on the morning of the test
- Undergone major medical/surgical event needing hospitalization within the preceding 3 months
- Presence of disease or drug influencing digestion and absorption of medicine

Glycemic response associated with consumption of the common bean product will be assessed in 10 T2DM patients in Makueni County. The participants will be recruited from the **Makueni Level-5 and Mbooni sub-county hospitals** which run a diabetes outpatient clinic.

Inclusion criteria:

- Male or female aged 18-69 years
- Previously diagnosed with type 2 diabetes
- Consenting to participate

Exclusion criteria:

- Use of prescription medication
- History of eating disorders and irregular eating habits
- Use of tobacco or alcohol
- Females experiencing menstrual period or adverse premenstrual symptoms

For the reference food, we will use either anhydrous glucose powder, 50g or dextrose (glucose monohydrate), 55g. The reference food will be dissolved in 250ml of water and refrigerated for use within 72 hours after preparation. Participants will be fed with an equi-carbohydrate portion of the common bean product to the reference food.

² Stable doses of oral contraceptives, acetylsalicylic acid, thyroxin, vitamins and mineral supplements or drugs to treat hypertension or osteoporosis are acceptable

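### Section 7.1 sets a food allergy and intolerance criterion for the healthy volunteers but not for the type 2 diabetes patients, who eat the same novel bean product

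*Combined protocol and SAP*

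**What the plan says.** Section 7.1 gives two separate eligibility lists.

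- **Healthy volunteers (10, at the university hospital).** Three inclusion and five exclusion criteria. One inclusion criterion is "No known food allergies or intolerances".
- **Type 2 diabetes patients (10, from two hospital clinics).** Three inclusion criteria: age, consent and "Previously diagnosed with type 2 diabetes". Four exclusion criteria: "Use of prescription medication", "History of eating disorders and irregular eating habits", "Use of tobacco or alcohol", and current menstruation or premenstrual symptoms. Allergy and intolerance do not appear.

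The patients are fed the product: "Glycemic response associated with consumption of the common bean product will be assessed in 10 T2DM patients in Makueni County". Section 7.2 refers back to section 7.1 for the eligibility criteria of the food insulin index and insulin response part and adds none of its own. Section 7.4 asks participants to finish the whole portion within 12 to 15 minutes.

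Section 8.1 cites Appendix 2 for both the index measurements and the response measurements, so the form serves both cohorts. Its first question is "Do you have a history of eating disorders and/or irregular eating habits". The other four concern tobacco or alcohol, menstruation, supplements and medication.

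**The concern.** By writing the criterion for one cohort, the plan treats allergy and intolerance as relevant to eating this product. It then leaves the criterion out for the other cohort and gives no reason. The exposure is the same kind in both: a full portion of a new bean-based food.

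What is at stake is mainly the safety of the patient cohort. Eligibility criteria are what recruiting staff apply, and under these a patient who reports a bean allergy does not fail any of them. There is a smaller consequence for the data: a patient who could not finish the portion or complete the session would be one of only 10.

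**Working it through.** No figure in the plan is in dispute and no formula applies. The check is an item-by-item comparison of the section 7.1 lists with Appendix 2.

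**Step 1. Patient list against the form.**

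| Patient criterion (section 7.1) | Type | Concerns allergy or intolerance? | Item in Appendix 2 |
|---|---|---|---|
| Age 18–69 | Inclusion | No | Date of birth |
| Diabetes diagnosis | Inclusion | No | None |
| Consent | Inclusion | No | None (signed separately) |
| Prescription medication | Exclusion | No | Question 5 |
| Eating disorder or irregular eating | Exclusion | No | Question 1 |
| Tobacco or alcohol | Exclusion | No | Question 2 |
| Menstruation or premenstrual symptoms | Exclusion | No | Question 3 |

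Allergy criteria in the patient list: 0 of 7. Take a patient who satisfies all seven rows and also has a known bean allergy: that patient is eligible as the rules stand.

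**Step 2. Does the form add the check?** Of the five yes/no questions, four match the four patient exclusions and the fifth (question 4, supplements) matches none of them. Allergy questions: 0 of 5. The form follows the patient list, so it also lacks an item for the allergy criterion that does apply to the healthy volunteers.

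**Step 3. Healthy list against the form.**

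| Healthy-volunteer criterion | Item in Appendix 2 | Coverage |
|---|---|---|
| Age 18–69 | Date of birth | Covered |
| No medication affecting glucose | Question 5 | Covered |
| Past diabetes, or glucose-lowering drugs | Question 5 for drugs; no history question | Partial |
| Alcohol or tobacco the evening before | Question 2 (current use); drinks in the 24-hour recall | Partial |
| Disease or drug affecting digestion | Question 5 for drugs; no disease question | Partial |
| Food allergy or intolerance | None | No item |
| "Vigorous exercise on the morning of the test" | None | No item |
| Hospital stay for a major event in the last 3 months | None | No item |

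Total: 2 covered + 3 partial + 3 with no item = 8.

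**Step 4. Is there a check elsewhere?** Section 8.2 says enumerators help with screening but describes no instrument. The risk text in section 8.6 covers catheter discomfort and referral after unforeseen events. Section 11 names no risk from the product. Appendices 1a and 1b (information sheets and consent forms) were not available.

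**Step 5. Size.** If the same people serve the glucose and insulin parts, the criterion covers 10 of 20 participants. If section 7.2 means separate recruits, it covers 20 of 40. Either way it is half.

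**The case against.** The best defence is that the text reviewed is not the whole process. Screening is named in section 8.2 as an activity in its own right, and the information sheets and consent forms were not available. Appendix 2 is titled a questionnaire for the response study and records catheter and eating times, so it is a test-day data sheet; its role in screening is an inference from its match to the patient exclusions. A known allergy is by definition known to the patient, who receives an information sheet and signs consent. Testing takes place at hospitals, with referral to casualty if something goes wrong.

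Much of this stands, and it limits what can be said. Three stronger readings are tempting, and the documents do not support them:

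- **That several healthy-volunteer criteria are never checked.** The available text shows only that no check is documented there. Recent hospital stays or digestive disease could be settled at recruitment, before this form is used.
- **That four or more healthy-volunteer criteria have no form item.** Step 3 gives three with none and three partly covered. Digestive disease is one half of a criterion whose drug half is reached by question 5.
- **That test-day conditions are uncontrolled.** Section 7.4 gives instructions on alcohol, physical activity, the evening meal and fasting, fixes the arrival time and has participants tested at rest. The 24-hour recall can pick up drinks from the evening before. These are not recorded eligibility checks, but they are controls.

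None of this closes the gap in the patient list. A warning on a consent page or a question at screening would not make allergy a criterion in section 7.1, and staff would have no written rule to apply to the answer.

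**Conclusion.** The point holds for the allergy and intolerance criterion. Section 7.1 applies it to one of two cohorts eating the same product, section 7.2 carries the asymmetry into the insulin part, and no allergy check is documented in the available text for either cohort. Half of those who eat the product are outside the criterion.

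The eligibility gap can be read directly from section 7.1 and needs no assumption about missing pages. The statement about checks is weaker: it is limited to the available text and depends on what the consent pages and any screening record contain. The documents give no rate of bean allergy or intolerance, so no event frequency is claimed. Sample size, the index calculations and the planned analyses are unaffected. The inconsistency should be resolved before patients are fed, because it bears on safety and is cheap to correct.

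**What to change.** 1. Reconcile the two lists in section 7.1 so that the plan's own allergy and intolerance criterion is addressed for everyone who eats the product. If its absence from the patient list is deliberate, state this with the reason. Section 7.2 then follows by its existing cross-reference.
2. Add one yes/no item on known food allergy or intolerance to Appendix 2, beside the five existing questions, to be answered before feeding. If eligibility is recorded in a separate screening document, name that document.

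The cost is one eligibility bullet and one form line. At most an occasional patient would be excluded; that this would be rare is an assumption, since the documents give no rate. Further items for the other healthy-volunteer criteria (hospital stay, digestive disease, evening tobacco or alcohol, morning exercise) would be useful record-keeping but are optional.

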Appendix 3: VAS in assessment of appetite sensations

| | | |
|---------------------|---|-----------------------------|
| Not at all hungry | How hungry do you feel? | Extremely hungry |
| Not at all full | How full do you feel? | Extremely full |
| Not at all satiated | How satiated are you? | Extremely satiated |
| Not at all strong | How strong is your desire to eat? | Extremely strong |
| Nothing at all | How much could you eat right now? | A very large amount of food |
| Yes, very much | Would you like to eat something sweet? | No, not at all |
| Yes, very much | Would you like to eat something salty? | Yes, very much |
| Yes, very much | Would you like to eat something fatty? | Yes, very much |

Hunger: A compelling need or desire for food; the painful sensation or state of weakness caused by the need of food

Satiety: Fullness that persists after eating; length of time until next eating occasion

This certificate reflects that Sponsor, not TransCelerate BioPharma, certifies that an investigator and/or trainee has completed training meeting the Minimum Criteria to facilitate mutual recognition of site training and qualification. This is not a legal document, and does not certify compliance with any applicable laws or regulations. A list of GCP Training Solutions meeting the minimum criteria is maintained on TransCelerate's website <http://transceleratebiopharmainc.com>.

*TransCelerate BioPharma, Inc. Operating Principles for ICH GCP Investigator Training 7 February 2013, version 1.1

Appendix 7: Adherence measures COVID 19 prevention and control regulations (adopted from Ministry of Health, Kenya)

Considering that the COVID-19 disease has now been classified as a pandemic we are taking the following precautionary measures during research activities:

1. Regular and thorough washing of hands with soap and water, or alcohol-based hand sanitizer provided by the researches.
2. Maintaining a distance of at least 1 meter (5 feet) between yourself and anyone (who is coughing or sneezing), avoiding handshakes or hugging.
3. Persons with a cough or sneezing should stay home or keep a social distance, but avoid mixing with others in a crowd.
4. Maintain good respiratory hygiene by covering your mouth and nose while coughing and sneezing with a handkerchief, tissue, or into flexed elbow.
5. Stay at home if you feel unwell with symptoms like fever, cough and difficulty in breathing.
6. All study participants should at all times wear a face mask to reduce the chances of transmission of the virus.
7. Any cases regarding the disease will be reported using the call line facility number 719. Correct messages to be relayed to the participants (if need be) will be received from *719#
8. Surfaces used during the research activities (e.g. desks, tables) and objects will be wiped with disinfectant regularly.
